19.8. Confidentiality

The trial staff will ensure that the participants' anonymity is maintained. All documents will be stored securely and be accessible to trial staff and authorised personnel only. In the future, with the consent of the participants, or parents/guardians in the case of a child, anonymized specimens and data may be shared with other research groups.

20. SAMPLE SHARING AND STORAGE

Samples collected will be used for the purpose of this study as stated in the protocol and stored for future use. Consent will be obtained from subjects for sample storage and/or shipment of specific samples to collaborating institutions for investigations that cannot be performed locally. Any proposed plans to use samples other than for those investigations detailed in this protocol will be submitted to the relevant ethics committees prior to any testing. Material transfer agreements will be arranged and signed where appropriate/needed.

21. DATA HANDLING AND RECORD KEEPING

All study data will be recorded on standard Case Report Forms (CRF) and entered to MACRO EDC®, a GCP-compliant data management system. The database is password-protected and includes internal quality checks to identify data that appear inconsistent, incomplete, or inaccurate.

Study participants will be identified by a unique participant number in the database. The study data management plan outlines all activities that will be carried out to ensure security and quality of the data.

Subject records at site will, taking into account the ability of the sites, be stored in binders or scanned and stored electronically. The records will be retained until the youngest child participating in the trial reaches 21 or five years following completion of the study, whichever is longer. The study database will be retained indefinitely.

With participant's consent, participant's data and results from blood analyses stored in the database may be shared according to the terms defined in the MORU data sharing policy with data repositories such as the WorldWide Antimalarial Resistance Network (WWARN, terms of submission here: <http://www.wwarn.org/tools-resources/terms-submission>) or other researchers to use in the future. All personal information will be anonymised so that no individual can be identified from their treatment records, through interviews, or from mapping data.

22. SPONSORSHIP AND INSURANCE

The University of Oxford is the study sponsor and has a specialist insurance policy in place, which would operate in the event of any participant suffering harm as a result of their involvement in the research (Newline Underwriting Management Ltd, at Lloyd's of London).

23. PUBLICATION POLICY

Any data published in the peer-reviewed medical literature will protect the identity of the subjects. This trial will be registered in a web based protocol registration scheme. All those who have made a substantial contribution will be co-authors on publications. The sites have the right to publish their data individually and to include members of the sponsor's team who have made a significant contribution. There will also be publications of pooled data which will be coordinated by the MORU group. All sites will have the opportunity to contribute to these publications.

All the research findings from the programme and from relevant research outside the Programme will be analysed and integrated, and through the WWARN site and the WHO Global Malaria Programme will be disseminated to policy makers, National Malaria Control Programmes (NMCPs) and other researchers.

25. APPENDIX 1. STUDY SCHEDULE

DeTACT-Africa project clinical activity schedule																																		
Test/application	SCR	D0						D1						D2						D3				D7	D14	D21	D28	D35	D42	D49	D56	D63	DRE C	Unsc h.
		H0	H4	H6	H8	H12	H18	H24	H28	H30	H36	H42	H48	H52	H54	H60	H64	H66	H72	H78	H84	H90	H168											
Verbal consent (if applicable)	X																																	
Informed consent	X																																	
Demographic data/Medical history	X	X																																
Place of residence, work, travel history and data on mobile phone use		X																												X				
Drug history	X	X																																
Temperature (until 2 measurements<37.5)	X	X		X		X	X	X		X	X	X	X		X	X		X	X	X	X	X	X	X	X	X	X	X	X	X	X			
Vital signs	X	X						X				X							X				X	X	X	X	X	X	[X]	[X]	[X]	X	[X]	
Pregnancy test for females of child bearing potential (Gambia, Rwanda)	X																													X				
Height/weight	X	X																													X			
MUAC and other assesments of nutritional status	X	X																																
Symptom questionnaire		X							X			X							X				X	X	X	X	X	X	[X]	[X]	[X]	X	[X]	
Physical examination	X	X						X			X								X				X	X	X	X	X	X	[X]	[X]	[X]	X	[X]	
Randomisation to study drug		X																																
Study drug administration (ASMQ+/-PPQ) (no fat)		X						X			X																							
Study drug administration (AL+/-AQ) (with fat)		X			X			X		X	X				X																			
Study drug administration (Primaquine)								X																										
Electrocardiographic recording		X	X																													X		

(X) On day 49, 56 and 63 follow up will in principle consist of temperature measurement, blood smear. Additional examinations may be performed at the discretion of the clinician.
 {X} ECG will be performed at H52 for patients in the ASMQ+/-PPQ arms and at H64 for the AL+/- AQ arms.
 If a recurrent infection is found or the subject reports symptoms spontaneously additional procedures will be performed:
 Temperature, Vital signs, Symptom questionnaire and Physical examination

DeTACT-Africa project blood sampling schedule (Children)																																				
Sampling type and volume (ml)	SCR	D0						D1					D2						D3				D7	D14	D21	D28	D35	D42	D49	D56	D63	DRE C	Unsc h.	Total (ml)		
		H0	H4	H6	H8	H12	H18	H24	H28	H30	H36	H42	H48	H52	H54	H60	H64	H66	H72	H78	H84	H90	H168													
Blood smear (*)	0.5	0.5 (Hb, Hct only if FBC not done)		0.5		0.5	0.5	0.5			0.5							0.5 (Hb, Hct only if FBC not done)				0.5 (Hb, Hct only if FBC not done)		0.5	0.5		0.5 (Hb, Hct only if FBC not done)	0.5	0.5	0.5	0.5	0.5	0.5	0.5	(*)	9.5
HCT (EDTA)																																				
Hb (EDTA)																																				
Dried Blood Spot (EDTA) (aliquot of blood collected for microscopy)																																			0	
In vitro/ex vivo sensitivity assays (Heparinized)		2																																2	4	
DNA/RNA/Immunological assessments (EDTA/Heparin)		5		1		1		1				1											1	1	1	1	1	1	1				5	21		
PK sampling (**)		1		1				1					0.5			0.5							1	1		1						1	8			
Biochemistry (heparinised blood)		1																	1				1			1								4		
Full blood count (EDTA)		0.5																				0.5				0.5								2		
Total volumes per time point (ml)	0.5	10	0	2.5	0	1.5	0.5	2.5	0	0	0.5	0	1.5	0.5	0	0	0.5	0	3	0	0	0	4	1.5	2.5	3	2.5	1.5	0.5	0.5	0.5	8.5	0	48.5		

* Patients with >5000 parasites/ μ L at inclusion will have blood smears at 6h, 12h, 18h, 24h and thereafter every 12 hours until parasite clearance (when two consecutive blood smears are negative) even if blood smears stay positive longer than 72h. In all cases, blood smears must be collected at 24h, 48h, 72h and then at all visits, including unscheduled visits. If parasitemia <=5000 parasites/ μ L at inclusion, blood smears must still be performed at 24h, 48, and 72h.

** Day 0, day 7 and day of recurrence samples will be obtained in all subjects. In 500 subjects, two samples will be taken at a random timepoint in the first 72 hours and two samples will be taken at a random timepoint in the first 42 days. In NIGER ONLY, an additional sample of 1 mL will be collected at a random timepoint between D0H0 & D7 from all subjects included at the site. Accordingly, the maximum blood volume from children recruited at the NIGER SITE ONLY will be 49.5 mL.

PK samples have been included in this table to calculate the total volume of blood to be collected but may not be collected at the time-points indicated on this table (e.g., H6, H64, D21, D35 PK samples). An additional PK sample of 1 mL will be collected at H52 or at H64 but has been included in this table as 0.5 mL at both time-points, again to calculate the total volume.

DeTACT-Africa project blood sampling schedule (For Gambia, Rwanda sites only: Subjects \geq 12 years)																																				
Sampling type and volume (ml)	SCR	D0						D1					D2						D3				D7	D14	D21	D28	D35	D42	D49	D56	D63	DRE C	Unsc h.	Total (ml)		
		H0	H4	H6	H8	H12	H18	H24	H28	H30	H36	H42	H48	H52	H54	H60	H64	H66	H72	H78	H84	H90	H168													
Blood smear (*)	0.5	0.5 (Hb, Hct only if FBC not done)		0.5		0.5	0.5	0.5			0.5							0.5 (Hb, Hct only if FBC not done)				0.5 (Hb, Hct only if FBC not done)		0.5	0.5		0.5 (Hb, Hct only if FBC not done)	0.5	0.5	0.5	0.5	0.5	0.5	0.5	(*)	9.5
HCT (EDTA)																																				
Hb (EDTA)																																				
Dried Blood Spot (EDTA) (aliquot of blood collected for microscopy)																																			0	
In vitro/ex vivo sensitivity assays (Heparin)		3																																3	6	
DNA/RNA/Immunological assessments (EDTA/Heparin)		10		1		1		1				1											1	2	2	2	2	2	2				10	37		
PK sampling (**)		1		1				1					0.5			0.5							1	1		1						1	8			
Biochemistry (heparinised blood)		1																	1				1			1								4		
Full blood count (EDTA)		0.5																				0.5				0.5								2		
Total volumes per time point (ml)	0.5	16	0	2.5	0	1.5	0.5	2.5	0	0	0.5	0	1.5	0.5	0	0	0.5	0	3	0	0	0	5	2.5	3.5	4	3.5	2.5	0.5	0.5	0.5	14.5	0	66.5		

* Patients with >5000 parasites/ μ L at inclusion will have blood smears at 6h, 12h, 18h, 24h and thereafter every 12 hours until parasite clearance (when two consecutive blood smears are negative) even if blood smears stay positive longer than 72h. In all cases, blood smears must be collected at 24h, 48h, 72h and then at all visits, including unscheduled visits. If parasitemia <=5000 parasites/ μ L at inclusion, blood smears must still be performed at 24h, 48, and 72h.

** Day 0, day 7 and day of recurrence samples will be obtained in all subjects. In 500 subjects, two samples will be taken at a random timepoint in the first 72 hours and two samples will be taken at a random timepoint in the first 42 days.

For Gambia, RWanda Sites only: A urine pregnancy test will also be performed at screening and at D63 for women of child-bearing age.

PK samples have been included in this table to calculate the total volume of blood to be collected but may not be collected at the time-points indicated on this table (e.g., H6, H24, D21, D35 PK samples). An additional PK sample of 1 mL will be collected at H52 or at H64 but has been included in this table as 0.5 mL at both time-points, again to calculate the total volume.

26. APPENDIX 2. DOSING SCHEDULES

Artemether-lumefantrine + amodiaquine or placebo

Artemether-lumefantrine + Amodiaquine (or placebo) dosing schedule			
Body weight (kg)	Dose administered at 0h, 8h, 24h, 36h, 48h, 60h		
	Artemether (mg)	Lumefantrine (mg)	Amodiaquine (mg) / PBO
5 to 9.9	20	120	40 / 0
10 to 15.9	40	240	80 / 0
16 to 29.9	60	360	120 / 0
30 to 54.9	100	600	200 / 0
≥ 55	120	720	240 / 0

Artemether-lumefantrine +/- Amodiaquine (or placebo) dosing schedule		
One tablet of AL contains 20 mg artemether and 120 mg lumefantrine; One tablet of AQ contains 40 mg amodiaquine; Placebo contains no active pharmaceutical ingredient.		
Body weight (kg)	Number of tablets per timepoint (0h, 8h, 24h, 36h, 48h, 60h)	
	AL	Amodiaquine / PBO
	Tablets	Tablets
5 to 9.9	1	1
10 to 15.9	2	2
16 to 29.9	3	3
30 to 54.9	5	5
≥ 55	6	6

Artesunate-mefloquine + piperazine or placebo

Artesunate-mefloquine + piperazine (or placebo) dosing schedule			
Body weight (kg)	Dose administered at 0h, 24h, 48h		
	Artesunate (mg)	Mefloquine HCl (mg)	Piperazine TP (mg) / PBO
5 to 10.9	32	70	160 / 0
11 to 17.9	64	140	320 / 0
18 to 33.9	100	220	500 / 0
34 to 64.9	200	440	1000 / 0
≥ 65	300	660	1500 / 0

Artesunate-mefloquine + piperazine (or placebo) dosing schedule			

One Paediatric tablet of AS contains 32 mg artesunate, one Adult tablet contains 100 mg; One Paediatric tablet of MQ contains 70 mg mefloquine, one Adult tablet contains 220 mg; One Paediatric tablet of PPQ contains 160 mg piperazine, one Adult tablet contains 500 mg; Paediatric and Adult placebos contain no active pharmaceutical ingredient.
			
Body weight (kg)	Number of tablets per timepoint (0h, 24h, 48h)		
	Artesunate	Mefloquine HCl	Piperazine TP / PBO
	Tablets	Tablets	Tablets
5 to 10.9	1 (Paed)	1 (Paed)	1 (Paed)
11 to 17.9	2 (Paed)	2 (Paed)	2 (Paed)
18 to 33.9	1 (Adult)	1 (Adult)	1 (Adult)
34 to 64.9	2 (Adult)	2 (Adult)	2 (Adult)
≥ 65	3 (Adult)	3 (Adult)	3 (Adult)

Primaquine

Primaquine dosing schedule			
One tablet of Primaquine contains either 7.5 or 15 mg of Primaquine			
Body weight (kg)	Dose administered at 24 h		
	Primaquine (mg)	7.5 mg tablet	15 mg tablet
<25	3.75	0.5	0.25
25 – 50	7.5	1	0.5
>50	15	2	1

---

**STATISTICAL ANALYSIS PLAN**

---

## STATISTICAL ANALYSIS PLAN

### 1. Analysis Considerations

#### 1.1 General Analysis Approach

The main analysis strategy for the primary outcome will be the intention-to-treat (ITT) principle. In this analysis, patients will be analysed according to the arm of randomisation irrespective of the treatment that was actually given. Complete Case Analysis will be used in the ITT analysis population (Groenwold et al 2012; Mukaka et al 2016; Sullivan et al 2018). Furthermore, the estimates of efficacy using survival analysis will be done. This approach will help in handling missing data as all patients will be included in the analysis and censored at their last follow-up time. These ITT analyses will be followed by the per protocol (PP) analysis. In this analysis only those that adhered to the protocol with respect to the primary outcome will be included for analysis of the primary outcome.

Key secondary endpoints such as parasite clearance parameters (e.g. half-lives), safety and tolerability data will be analysed similar to the ITT approach for the main primary outcome. In this analysis, patients will be analysed according to the arm of randomisation irrespective of the treatment that was actually given and all patients will be included in the analyses irrespective of their follow-up status as long as they have the data. Withdrawals and losses to follow up will not affect the analyses of this data as long as the relevant data needed for these analyses is available prior to withdrawal or loss to follow up.

Data analysis will mainly be performed using Stata 17 or higher, StataCorp, [name] or in R software.

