15. STATISTICAL CONSIDERATIONS

15.1. Sample size justification

These studies will have a non-inferiority trial design. Each site will be powered for the efficacy endpoint. For the safety and tolerability endpoint, the sample size will be pooled across the study

sites to achieve the desired power of at least 80% to detect rare events.

For sample size calculations, the following assumptions have been used: The expected efficacy of ACTs (AL, ASMQ) in these countries is expected to be approximately 96%. The matching TACT efficacy is assumed to be at least 90% under the null hypothesis of inferiority based on the WHO 90% efficacy threshold. However preliminary TRACII study data suggest that TACTs potentially may have a better efficacy of 1% to 2% higher in favour of TACT (i.e. a conservative 97%-98% efficacy or higher).

A one-sided alpha of 0.025 has been used in sample size calculations as non-inferiority is in one direction. For the efficacy outcome, a sample size of 60 subjects in the ACT plus placebo arms and 120 subjects in the matching TACT would be needed to achieve approximately 80% power to detect a non-inferiority margin difference between the group efficacy of -6%. With an additional 20% to cover for loss to follow up, we would therefore need 72 subjects in ACT plus placebo group and 144 subjects in the matching TACT in each of the sites. Since there will be 4 arms, it means we will need 432 subjects per site with 144 subjects in the two ACT arms combined and 288 subjects in the two TACT arms combined.

The sample sizes are in the ratio of 1:2 for ACT vs TACT to allow us to collect more safety and tolerability data for TACTs, which could be beneficial to both policy makers as well as future malaria patients [26, 27]. With these numbers of recruited subjects in Africa, we will have a power above 80% to detect an increase of the incidence of adverse events from 1 in 100 to 3 in 100 for subjects treated with ACT as compared to the matching TACT, respectively.

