19.4.5. Risks of new partner drug combinations

No interactions between lumefantrine and amodiaquine or piperazine and mefloquine are expected. Based on the relatively safe and limited side effect profiles of both drugs, no life-threatening interactions between lumefantrine and amodiaquine are expected. Also no life-threatening interactions between piperazine and mefloquine are expected.

In addition, the preliminary results of the TRACII trial indicate that the TACTs artemether-lumefantrine+amodiaquine and DHA-piperazine+mefloquine have a good safety and tolerability profile, although both TACTs were found to induce slightly higher vomiting rates within the first hour after administration of the study drugs, compared to their matching ACTs. The safety profile of ASMQ +/- PPQ is expected to be similar to that of DHA-PPQ +/- MQ.

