#### 2.1.3. Secondary objectives and endpoints

- To compare the safety and tolerability of ACTs and TACTs within and across sites and regions, including comparisons of 'non-matching' ACTs vs TACTs (AL+Placebo versus ASMQ+PPQ, ASMQ+Placebo versus AL+AQ).
  - Incidence of adverse events and serious adverse events within the first 42 days including markers of hepatic, renal or bone marrow toxicity; cardiotoxicity, in particular QT or QTc-interval above 500 ms at timepoint H4 and H52/H64 and between these time points; change from baseline in haemoglobin at days 3, 7, 28, stratified for G6PD status/genotype; proportion of subjects requiring retreatment due to vomiting within 1 hour after administration of the study drugs; proportion of subjects that reports completing a full course of observed TACT or ACT without withdrawal of consent or exclusion from study because of drug related serious adverse event
  - Changes in the electrocardiogram (such as prolongation of the QTc-interval) in patients treated with TACT versus standard ACT
- To compare additional measures of treatment efficacy between treatment arms, including the 63-day ACPR, the post-treatment prophylactic effect of ACTs and TACTs defined as the 42-day & 63-day PCR uncorrected ACPR, gametocyte carriage, parasite clearance rates and fever clearance.

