### **3.4 Safety and tolerability of ACTs and TACTs within and across sites and regions, including comparisons of 'non-matching' ACTs vs TACTs (AL+Placebo versus ASMQ+PPQ, ASMQ+Placebo versus AL+AQ).**

Safety analyses will be based on the whole population that get administered the study drug. That is, the safety and tolerability data will be pooled from all the sites that received the same antimalarial treatment. Safety and tolerability of TACTs versus ACTs will be assessed by comparing the frequency (%) of adverse events and serious adverse events, with particular attention to abdominal pain, appetite perturbation, biochemical markers of hepatic and renal toxicity and QT interval prolongation, using the Fisher's exact test. Safety data will be presented in tabular and/or graphical format and summarized descriptively. Any clinically relevant abnormalities or values of potential clinically concern will be described. Patients will be analysed following the intention to treat analysis. All adverse event summaries will refer to treatment emergent adverse events, i.e. adverse events that newly started or increased in intensity after the study drug administration. Adverse events will be graded according to Division of AIDS table for grading the severity of ADULT AND PEDIATRIC adverse Events Version 2.0, November, 2014. The relevant DAIDS table will be appended to this document. The safety and tolerability summaries will be presented in tables 6.

The frequency and proportion of subjects that reports completing a full course of observed TACT or ACT without withdrawal of consent or exclusion from study because of drug related serious adverse events will be summarized within and across sites and regions. The 95% confidence intervals will be reported for the proportions. The proportions will be compared between matching drugs. The analyses will be summarised in table 7.

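### SAP 1.1's condition for ignoring losses to follow-up cannot be met for 42-day adverse-event incidence, and the SAP does not say how a child lost early without an event enters n and N

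*SAP*

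**What the plan says.** SAP 1.1 (General Analysis Approach) treats parasite clearance, safety and tolerability together. On inclusion it says that "all patients will be included in the analyses irrespective of their follow-up status as long as they have the data". On losses it continues: "Withdrawals and losses to follow up will not affect the analyses of this data as long as the relevant data needed for these analyses". The sentence ends with a condition on timing: these data must exist before the child withdraws or is lost.

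The safety endpoint in SAP 2.1.3 is "Incidence of adverse events and serious adverse events within the first 42 days". SAP 3.4 sets the population: "Safety analyses will be based on the whole population that get administered the study drug". The arms are compared by "comparing the frequency (%) of adverse events and serious adverse events", using Fisher's exact test. Table 6 has a row for the number of subjects and reports SAEs, symptoms and laboratory abnormalities as n/N (%) over the first 42 days.

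No safety section gives a censoring rule, person-time, or a rule for children with incomplete follow-up. Censoring is specified for efficacy only (SAP 1.1 and the missing-data part of SAP 3.3). Protocol 15.1 plans for loss: "With an additional 20% to cover for loss to follow up". That allowance is not split by arm or by day.

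**The concern.** The SAP 1.1 condition works for an endpoint that is complete before the child goes home. It fails for a 42-day incidence: a child last seen event-free on day 7 has unknown status for days 8 to 42, and nothing collected before the loss can supply it.

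Those later days matter. Adverse events are recorded at weekly visits from day 7 to day 42 (Protocol 9.5.4). Biochemistry and blood counts are taken on days 7 and 28 as well as earlier (Protocol 12.1.2), and there is an ECG on day 42 (Protocol 9.6).

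Two things are at stake. The absolute 42-day percentages would be too low in any arm that loses children. In addition, if one arm of a matching pair loses more children, the bias favours that arm, and for a safety comparison it is a poor error to leave unguarded.

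**Working it through.** **The plan's own safety figure.** Protocol 15.1 and SAP 2.2.1 claim power above 80% to detect 1 in 100 versus 3 in 100 with the Africa numbers. The arm sizes follow from 72 and 144 per matching pair per site:
- AL pair, 8 sites: 8 × 72 = 576 and 8 × 144 = 1152.
- ASMQ pair, 7 sites: 7 × 72 = 504 and 7 × 144 = 1008.
- Total: 576 + 1152 + 504 + 1008 = 3240, as stated.

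With two-sided alpha 0.05 (assumed, as none is stated for safety), the unpooled normal formula gives 86.7% and 81.9%, so the claim reproduces. With the planned Fisher's test the power is 77.8% and 70.6%. The point below does not depend on this figure.

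**Model.** R is the true 42-day risk of a first event, f the share of first events after day 7, and L the share of children lost at day 7. Loss is taken as unrelated to risk. R, f and L by arm are assumptions, because the documents give only 20% loss overall. If lost children stay in N, then

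expected crude percentage = R × (1 − f × L).

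**Equal loss, 20% in each arm, R = 10%.** The table would show 9.8% (f = 0.10), 9.5% (f = 0.25), 9.0% (f = 0.50) and 8.3% (f = 35/42 = 0.83, events spread evenly over 42 days). Both arms shrink by the same factor, so the ratio is 1.00.

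**Unequal loss, 10% ACT versus 20% TACT, equal true risk.** The apparent TACT/ACT ratio is (1 − 0.20f) / (1 − 0.10f) and does not depend on R:

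| f | Ratio | Shown at R = 10% (ACT vs TACT) |
|---|---|---|
| 0.10 | 0.98 / 0.99 = 0.99 | 9.9% vs 9.8% |
| 0.25 | 0.95 / 0.975 = 0.97 | 9.75% vs 9.5% |
| 0.50 | 0.90 / 0.95 = 0.95 | 9.5% vs 9.0% |
| 0.83 | 0.833 / 0.917 = 0.91 | 9.2% vs 8.3% |

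**Chance of a false significant result that TACT is safer** (576 versus 1152, pooled normal approximation, nominal 2.5%), at f = 0.50: 3.9% for R = 3%, 5.4% for R = 10%, and 9.8% for R = 30% (28.5% versus 27.0% shown).

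**Effect of censoring.** Take R = 10% and f = 0.50. The risk to day 7 is 5%. The risk after day 7 among those still event-free is 5/95 = 5.26%. Kaplan-Meier gives 1 − 0.95 × 0.9474 = 10.0% whatever L is, because lost children leave the risk set. A simulation of 2 million children per scenario agrees: crude 9.5% and 9.0% with 10% and 20% lost, Kaplan-Meier 10.0% in both.

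**The case against.** **The SAP statement is conditional.** A reader might infer from its first half that the SAP calls losses harmless without qualification. It does not: the condition about data available before loss is part of the sentence. What stands against the SAP is narrower, namely that the condition cannot be satisfied for this endpoint.

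**Keeping the lost child in N is inferred, not written.** SAP 1.1 likens these analyses to the ITT approach, which uses complete cases, and limits inclusion to those who have the data. That could mean leaving out a child lost without an event. The all-treated population in SAP 3.4 and the layout of Table 6 point the other way and are the more natural reading. The exclusion reading is no safer. If event-free losses are dropped while early events are kept, then at R = 10%, f = 0.50, L = 20% the result is 9.0 / (100 − 20 × 0.95) = 9.0 / 81 = 11.1%, which is too high. Both readings mislead, and the SAP does not choose between them.

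**Nothing shows that loss will differ by arm.** A reader might infer that TACT will falsely look safer because "both TACTs were found to induce slightly higher vomiting rates within the first hour after administration of the study drugs" (Protocol 19.4.5). That vomiting occurs in hospital under observation, is recorded there, and is not evidence of later loss. ACT and TACT are blinded within each pair (Protocol 9.4), and adverse events or stopping study drug are in principle not reasons to leave the study (Protocol 11). A child who leaves because of intolerance will usually have had the event recorded first, and it still counts. This objection stands: the direction and existence of a between-arm bias are not established. It does not show that loss will be equal, and the SAP itself compares full-course completion without withdrawal between matching drugs (SAP 3.4, Table 7a).

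**The size depends on event timing.** If most first events fall in the dosing days, the effect is slight. This also stands, and is why a range is given.

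**Losses are already reported.** The CONSORT diagram in SAP 3.1 gives losses by arm. It does not give follow-up time for safety, and it does not change the estimate in Table 6.

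**Conclusion.** The point holds in a limited form. The SAP 1.1 reassurance cannot apply to 42-day adverse-event and SAE incidence, and the handling of children lost event-free before day 42 is undefined. If they stay in the denominator, the percentages are understated: at a true 10% with 20% lost at day 7, the table shows between 8.3% and 9.8%, depending on event timing. The between-arm ratio is unbiased under equal, non-informative loss. It falls to between 0.99 and 0.91 under an assumed 10% versus 20% loss at day 7. The documents do not support a claim that the safety comparison will be biased towards TACT.

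Endpoints completed in hospital are little affected, since children are admitted for at least 72 hours (Protocol 9). These are parasite clearance, QTc at H4 and H52/H64, retreatment for vomiting, and full-course completion. The figures rest on loss concentrated at day 7 and unrelated to risk. This is a cheap improvement to the SAP rather than a flaw that undermines the trial.

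**What to change.** 1. In SAP 1.1, limit the sentence on withdrawals and losses to endpoints completed in hospital: parasite clearance, QTc at H4 and H52/H64, retreatment for vomiting, and full-course completion. It need not be deleted.
2. In SAP 3.4 and Table 6, state how children with incomplete follow-up enter n and N. Keep n/N with Fisher's test as description.
3. For 42-day adverse-event and SAE incidence, add the cumulative incidence of first event by Kaplan-Meier (Aalen-Johansen where death competes), censored at last contact, with the difference between matching arms and its confidence interval.
4. State that this assumes non-informative loss. Censoring does not cure loss that depends on risk, so report follow-up time and the number lost before day 42 by arm beside it.
5. For the laboratory rows of Table 6, use as N the subjects with a sample at that visit.

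The cost is SAP wording and standard output from adverse-event and last-contact dates, with a method the SAP already uses for efficacy. No new data or procedures are needed. The downside is slightly more analysis work and slightly higher reported adverse-event percentages.
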